### **6.6.3. Vital Signs and Body Weight**

Vital signs (temperature (axillary), supine blood pressure and heart rate) and body weight will be presented using descriptive statistics. Criteria for potentially clinically important changes is shown in [Appendix 3](#).

#### **6.6.4. ECG**

Actual values and changed from baseline of all measured ECG parameters (an average of the triplicate measurements) will be presented using descriptive statistics. Frequencies and percentages of patients with potentially clinically important changes in ECG will be summarized. Criteria for potentially clinically important changes is shown in [Appendix 4](#).

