### 3.5.4. Electrocardiograms

Triplicate 12-lead (with a 10 second rhythm strip) tracings will be used for all electrocardiograms (ECGs). A QT interval will be corrected for an RR interval using Fridericia's (QTcF) and Bazett's factors (QTcB), respectively. Actually, QTcF will be reported by study sites. On the other hand, QTcB will be derived from  $QT / RR^{1/2}$ . A heart rate will be derived from  $60000 / RR$  if the unit of RR is msec.

At each time point, 3 consecutive ECGs will be performed at approximately 2 minutes apart to determine the mean QTcF and QTcB intervals.

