### **6.6. Safety Summaries and Analyses**

All safety analyses will be performed using the as-treated population.

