**Appendix 4. Criteria for Potentially Clinically Important Changes in ECG**

ECG Parameter	Criteria
Heart rate	Increase of >15 bpm from baseline value and $\geq 120$ bpm
	Decrease of >15 bpm from baseline value and $\leq 45$ bpm
PR interval	Change of $\geq 20$ msec from baseline value and $\geq 220$ msec
QRS interval	$\geq 120$ msec
QTcB interval	>500 msec
	Increase of >60 msec from baseline
QTcF interval	>500 msec
	Increase of >60 msec from baseline
	$\leq 450$ msec (Men) or $\leq 470$ msec (Women)
	>450 msec (Men) or >470 msec (Women)
Overall evaluation – center reported	Abnormal clinically significant

Abbreviations: bpm=beats per minute; PR interval=measure of the time between the start of the P wave and the beginning of the QRS complex; QRS=the part of the electrocardiogram comprising the Q, R, and S wave, together representing ventricular depolarization; QTc=corrected QT.

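### SAP Appendix 4 lists an unprolonged QTcF (at or below 450 msec in men, 470 msec in women) as a potentially clinically important ECG change, so any count of patients with at least one such change is 100% by construction

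*SAP*

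**What the plan says.** SAP 6.6.4 plans descriptive statistics for actual values and changes from baseline of all measured ECG parameters. It then adds that "Frequencies and percentages of patients with potentially clinically important changes in ECG will be summarized" and refers to Appendix 4, titled "Criteria for Potentially Clinically Important Changes in ECG". SAP 6.6 fixes the population: "All safety analyses will be performed using the as-treated population". The values are averages of triplicates; SAP 3.5.4 says that "3 consecutive ECGs will be performed at approximately 2 minutes apart to determine the mean QTcF and QTcB intervals".

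Appendix 4 gives four rows for QTcF:

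1. above 500 msec;
2. "Increase of >60 msec from baseline";
3. at or below 450 msec for men, or at or below 470 msec for women;
4. the complement of row 3, ">450 msec (Men) or >470 msec (Women").

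Nothing in 6.6.4 or in the notes under Appendix 4 marks row 3 as a reference category or removes it from the count. Nor does either place say whether the rows are reported only one by one, or also combined into a row for any criterion met. The SAP's version history (Table 1, version 2) gives consistency with study AV001 as the reason for adding these criteria.

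**The concern.** Row 3 is the normal side of a threshold, placed in a list of criteria for an important change. It is an absolute level, and nothing about it is either a change or a sign of prolongation. Because row 4 is its exact complement, the two together cover every possible QTcF value. A programmer who follows 6.6.4 and Appendix 4 literally and flags each patient who meets a listed criterion will flag everyone with a QTcF.

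The table deals with a risk that the protocol takes seriously: exclusion criterion 5 covers prolonged QTc, section 5.7.1 prohibits QT-prolonging drugs, and section 7.2.5 sets out follow-up of a prolonged QTcF. At stake is whether the summary of important ECG changes can be read as intended, and whether a line of normal values is mistaken for a safety finding.

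**Working it through.** The plan gives no figure for this point, so there is none to reproduce. The check is one of logic, followed by an illustration of size.

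**Inputs.** The four QTcF rows of Appendix 4, the counting rule in SAP 6.6.4, and the triplicate mean in SAP 3.5.4.

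**Step 1: coverage of the pair.** Let L = 450 msec for men and 470 msec for women. Row 3 is QTcF ≤ L and row 4 is QTcF > L. For any QTcF and either sex, exactly one is true, so the condition that at least one of rows 1 to 4 is met always holds.

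**Step 2: confirmation by enumeration.** The four rows were applied to QTcF from 300 to 600 msec in steps of 0.5 (601 values), change from baseline from −100 to +100 msec in steps of 5 (41 values), and both sexes: 601 × 41 × 2 = 49,282 combinations.

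- Meeting at least one QTcF criterion: 100%.
- Meeting exactly one of rows 3 and 4: 100%.

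**Step 3: comparison with neighbouring criteria.**

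| Block | Row for the normal side of a threshold? |
|---|---|
| Appendix 4, QTcB | No; only above 500 msec and increase above 60 msec |
| Appendix 4, heart rate, PR, QRS, overall evaluation | No |
| Appendix 3, vital signs and weight | No |
| Appendix 4, QTcF | Yes, row 3 |

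Row 3 is the only one of its kind in either appendix.

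**Step 4: what the count would be without row 3.** The documents give no QTcF distribution, so this step is an assumption. Take a normal distribution for a single reading, with the same mean and SD for both sexes. The share above the limit is 1 − Φ((L − mean)/SD).

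| Assumed mean / SD (msec) | Men, above 450 | Women, above 470 |
|---|---|---|
| 400 / 20 | z = 2.5, 0.6% | z = 3.5, 0.02% |
| 410 / 20 | z = 2.0, 2.3% | z = 3.0, 0.13% |
| 420 / 25 | z = 1.2, 11.5% | z = 2.0, 2.3% |

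At one reading the row 4 share is then about 0.6% to 11.5% in men and 0.02% to 2.3% in women, against a fixed 100% for a combined count that keeps row 3. The chance that a patient is ever above the limit over several visits would be higher than these single-reading shares.

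**The case against.** The strongest reply is that 6.6.4 defines no combined row. Appendix 4 lists criteria by parameter, and the QTcF rows are nested (above 500 msec lies inside above 450/470 msec), which suits a line-by-line display. On that display rows 1, 2 and 4 are unaffected and row 3 merely shows the remainder. The pair may have been a deliberate category display carried over from study AV001, whose tables cannot be seen here. This stands as far as it goes: the 100% applies to rows 3 and 4 taken together, or to a count of any criterion met, and not to each line.

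A reader might go further and infer that the planned analysis will carry no information about QT prolongation. The documents do not support that. Actual values and changes are summarised for every ECG parameter (SAP 6.6.4), QTcB has its own rows without the pair, and the Cardiac category in SAP Appendix 2 includes the torsade de pointes/QT prolongation query. Management of individual patients under protocol 7.2.5 uses its own thresholds and does not depend on Appendix 4.

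What the reply does not remove is the wording. Appendix 4 calls row 3 a criterion for an important change, 6.6.4 tells the analyst to count patients with important changes, and no text says otherwise. As a category display the pair is also incomplete: ECGs are repeated over the study, and the SAP does not say whether the rows apply by visit or to the worst value on treatment. A patient on both sides of the limit at different visits would fall in both rows.

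**Conclusion.** The point holds as a minor error in a reporting rule. As written, every patient with an evaluable QTcF meets at least one QTcF criterion, so any count of patients with at least one important QTcF or ECG change is 100% of them by construction, and unprolonged values sit under an important-change heading. The 100% follows from the criteria alone and needs no assumption about QTcF values, but it requires a recorded sex and an evaluable QTcF, so it does not extend to a patient whose ECG yields no QTcF. It appears as a headline figure only if criteria are combined; with separate lines, those for above 450/470 msec, above 500 msec and an increase above 60 msec keep their meaning. Only a descriptive safety table is affected. The primary analysis, its decision rule and the efficacy endpoints are untouched.

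**What to change.** In SAP Appendix 4, do one of the following:

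- remove the row for QTcF at or below 450 msec (men) or 470 msec (women) from the important-change criteria; or
- keep the category for alignment with study AV001, but label it as the reference category, exclude it from the count, and show it in a separate QTcF category table.

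In either case, count patients on the QTcF criteria already listed: above 450/470 msec, above 500 msec, and an increase of more than 60 msec from baseline. One added sentence in SAP 6.6.4 should say whether a row for any criterion met is produced, and whether the criteria apply by visit or across all post-baseline values.

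The cost is one row or label in an appendix and one sentence in the text. No new data are needed, and no clinical rule changes.

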4.2. Exclusion Criteria

Patients with any of the following characteristics/conditions will not be included in the study:

1. Any prior medical treatment for CML, including TKIs, with the exception of hydroxyurea treatment, which is permitted for up to 6 months prior to registration.
2. Any past or current CNS involvement, including leptomeningeal leukemia.
3. Extramedullary disease only.
4. Major surgery or radiotherapy within 14 days prior to registration.
5. History of clinically significant or uncontrolled cardiac disease including:
 - History of, or active, congestive heart failure;
 - Uncontrolled angina or hypertension within 3 months prior to registration;
 - Myocardial infarction within 12 months prior to registration;
 - Clinically significant ventricular arrhythmia (such as ventricular tachycardia, ventricular fibrillation, or Torsades de pointes);
 - Diagnosed or suspected congenital or acquired prolonged QT interval history or prolonged QTc (QTcF should not exceed 500 msec);
 - Unexplained syncope.
6. Patients with active, uncontrolled bacterial, fungal, or viral infection, including hepatitis B virus (HBV), hepatitis C virus (HCV), known human immunodeficiency virus (HIV) or acquired immunodeficiency syndrome (AIDS)-related illness.
7. Recent or ongoing clinically significant GI disorder (eg, Crohn's disease, ulcerative colitis, or prior total or partial gastrectomy).
8. History of another malignancy within 5 years prior to registration with the exception of basal cell carcinoma or cervical carcinoma in situ or Stage 1 or 2 cancer that is

considered adequately treated and currently in complete remission for at least 12 months.

9. Uncontrolled hypomagnesemia or uncorrected hypokalemia due to potential effects on the QT interval.
10. Known prior or suspected severe hypersensitivity to study drugs or any component in their formulations.
11. Investigator site staff members directly involved in the conduct of the study and their family members, site staff members otherwise supervised by the investigator, or patients who are Pfizer employees, including their family members, directly involved in the conduct of the study.
12. Participation in other studies involving investigational drug(s) within 30 days or 5 half-lives of investigational product, whichever is longer, prior to registration and/or during study participation.

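### Four absolute ECG criteria are reported as changes with no baseline condition, so a stable pre-dose abnormality can be counted as a change

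*SAP*

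**What the plan says.** SAP 6.6.4 plans two ECG displays. The first is continuous: "Actual values and changed from baseline of all measured ECG parameters (an average of the triplicate measurements) will be presented using descriptive statistics". The second is a count: "Frequencies and percentages of patients with potentially clinically important changes in ECG will be summarized". The criteria for the count are in SAP Appendix 4, and they are of two kinds.

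- **Tied to baseline:** the heart-rate rows (for example "Increase of >15 bpm from baseline value and $\geq 120$ bpm"), the PR row, and the rows for a QTcB or QTcF increase of more than 60 msec.
- **Absolute:** QRS of at least 120 msec; QTcB above 500 msec; QTcF above 500 msec; QTcF ">450 msec (Men) or >470 msec (Women"); and the centre-reported overall evaluation, "Abnormal clinically significant".

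Neither place excludes patients who met an absolute criterion before dosing, states the time window for the count, or plans an ECG shift table. The PR row asks for a change of at least 20 msec, without direction, together with a value of at least 220 msec.

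The only numeric ECG limit at entry is in Protocol 4.2, exclusion 5, which bars a diagnosed or suspected prolonged-QT history or "prolonged QTc (QTcF should not exceed 500 msec"). There is no QRS limit.

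**The concern.** A table headed as changes should count patients whose ECG changed. For the four rows at issue, the criterion is met just as well by a patient who arrives with, say, a stable wide QRS and leaves with the same QRS.

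The design makes this matter more. The Appendix 4 criteria were added for consistency with study AV001 (SAP Table 1, version 2). That study was randomised against imatinib, so pre-existing findings would be expected in both arms and a reader could compare them. The present study has one arm, and the count stands alone. ECGs are part of the secondary safety endpoint (Protocol section 2), and the protocol treats QT prolongation as a risk through its exclusions, prohibited medications and ECG rules. A percentage that mixes old and new findings would overstate how often abnormalities arise on treatment, by an amount the reader could not recover from the summary as specified.

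**Working it through.** The plan gives no ECG rate, so there is no stated figure to reproduce. The check is mainly a comparison of text.

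**Step 1. How the SAP treats baseline in its safety data.**

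| Data | Baseline handled? | Where |
|---|---|---|
| Adverse events | Yes: must begin or worsen after first dose | SAP 3.5.1 |
| Laboratory values | Yes: shift tables | SAP 6.6.2 |
| Potential Hy's Law cases | Yes: separate thresholds if raised at baseline | SAP 6.6.2.1 |
| Physical examination | Yes: change from screening | SAP 6.6.6 |
| ECG heart rate, PR, QTc increase above 60 msec | Yes | SAP Appendix 4 |
| ECG QRS, QTcF 450/470, QTcB 500, centre evaluation | No | SAP Appendix 4 |

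**Step 2. Can a patient enter already meeting one of these rows?**

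- QRS of at least 120 msec: no entry limit.
- QTcF above 450/470 and up to 500 msec: no numeric bar, although a known or suspected prolonged-QT history is excluded.
- QTcB above 500 msec: the entry limit is on QTcF only. At heart rates above 60 bpm (RR below 1 second) Bazett's correction gives the larger value, so QTcF can be within the limit while QTcB exceeds 500.
- Centre evaluation: no explicit bar, although the cardiac exclusions and investigator judgement (exclusion 13) should make it uncommon.
- QTcF above 500 msec: largely barred at entry, so this row is not part of the point.

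**Step 3. Size per patient.** Safety analyses use the as-treated population (SAP 6.6), planned at about 60 + 3 = 63. One stable pre-existing case adds 1/63 = 1.6 percentage points.

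**Step 4. Illustration, on assumed rates only.** Let *b* be the share meeting a criterion at baseline and *i* the new-onset rate among the rest, and suppose that baseline findings persist. The literal count gives *b* + (1 − *b*) × *i*. Among patients not meeting the criterion at baseline, the rate is *i*. The expected number of pre-existing cases is 63 × *b*, and the chance of at least one is 1 − (1 − *b*)^63.

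| *b* (assumed) | Expected pre-existing cases | Chance of at least one | Reported rate if *i* = 2% | Reported rate if *i* = 5% |
|---|---|---|---|---|
| 2% | 1.3 | 72% | 4.0% | 6.9% |
| 5% | 3.2 | 96% | 6.9% | 9.8% |
| 10% | 6.3 | over 99% | 11.8% | 14.5% |

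For example, with *b* = *i* = 5%: 0.05 + 0.95 × 0.05 = 0.0975, of which 0.05/0.0975 = 51% was present before dosing.

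**Step 5. The PR row.** A PR that shortens from 250 to 225 msec has changed by 25 msec and is still at least 220 msec. It satisfies the row as written, although it moved towards normal. The heart-rate rows avoid this by stating a direction.

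**The case against.** The strongest reply has five parts.

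1. **The SAP does not say that pre-dose abnormalities count as on-treatment findings.** A reader might infer that the table will present them as effects of bosutinib. The documents do not go that far: no window is stated, so the consequence is partly an inference from silence. Appendix 4 also lists QTcF at or below 450/470 msec, the complement of the 450/470 row. That suggests a display of levels, perhaps by visit with a baseline column. This stands as a limit on the claim. Even so, a by-visit display would show how many were abnormal before dosing, but not who became abnormal.

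2. **Entry rules are tighter than the 500 msec figure suggests.** A reader might infer that eligibility freely admits prolonged QT, or that the QTcF above 500 msec row is affected too. Neither is supported. Exclusion 5 removes a diagnosed or suspected prolonged-QT history and largely removes QTcF above 500 msec. QRS, QTcB and QTcF between 450/470 and 500 msec are still without a numeric bar.

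3. **Baseline-adjusted information is already planned.** Change-from-baseline summaries, the rows for an increase above 60 msec, and treatment-emergent cardiac and QT adverse events (SAP 6.6.1, Appendix 2) all help. This is true and reduces the weight of the point. None of them identifies a new QRS of 120 msec or more, or a new QTcF category.

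4. **The criteria were chosen to match AV001.** Comparability with that study is a good reason to keep the AV001-format count. It is no reason to omit a baseline-adjusted one.

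5. **No decision hangs on the table.** Formal testing is confined to the primary endpoint (SAP 5.1), the protocol's QTcF actions (Protocol 7.2.5) do not use Appendix 4, and the error would overstate harm. This also stands.

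**Conclusion.** The point holds as one of safety reporting. Four absolute rows sit in a summary of changes with no baseline condition, while comparable safety data in the same SAP are adjusted for baseline. A stable pre-dose abnormality can therefore be counted as a change, and a shortening PR can be as well.

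The firm figure is 1.6 points per affected patient, on the planned 63. How many patients are affected cannot be told from the documents. The 4.0% to 14.5% range in the illustration rests wholly on assumed baseline prevalence, assumed new onset and full persistence, and should not be read as a forecast. The documents do not show that the reported ECG rate will be materially inflated, only that the wording allows it and that the summary as specified would not reveal it. The primary analysis is untouched.

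**What to change.** In SAP 6.6.4 and Appendix 4:

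- For QRS of at least 120 msec, QTcF above 450/470 msec, QTcB above 500 msec and the centre evaluation, count patients who meet the criterion after the first dose and did not meet it at baseline as defined in SAP 3.4. Alternatively, add a baseline by worst post-baseline shift table for QTcF category, QRS and the overall evaluation.
- State the post-baseline window, the denominator, and how a missing baseline ECG is handled.
- Keep the AV001-format count beside the new display for comparability.
- In the PR row, require an increase of at least 20 msec from baseline, together with a value of at least 220 msec.

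The cost is some SAP wording and one extra table. Baseline ECGs are already scheduled, so no new data are needed. The baseline-adjusted rates may be lower than the AV001-format ones, so both should be clearly labelled.

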#### **6.6.5. Echocardiogram or Multiple Gated Acquisition**

Echocardiogram or multiple gated acquisition will be presented using descriptive statistics.

#### **6.6.6. Physical Examination**

Summary of physical examination will include the frequency and percentage of patients at the screening period by body sites. Presence or absence of any change from the screening will also be summarized using descriptive statistics at each post-screening visit.

#### **6.6.7. Death**

Deaths during the study and within 28 days from the last dose will be summarized by reason for death. Relevant information will also be supplied in a data listing. Deaths occurring beyond 28 days from the last dose will be included in a data listing.

### **7. INTERIM ANALYSES**

#### **7.1. Introduction**

##### **7.1.1. Interim Look**

An interim look (IL) will be conducted separately prior to the PA to assess the possibility of early communication with regulatory authorities based on the interim data. This will not be used to judge the early study termination or any changes of study design. The IL is planned only once in this study and the primary endpoint will not be analyzed.

##### **7.1.2. Primary Analysis**

The PA will be performed:

- To verify whether the study goal is achieved, and
- To submit study data to a regulatory authorities if the study drug is considered to show efficacy and tolerable.

All planned analyses will be performed at the PA unless otherwise specified. The PA is planned only once in this study. This study will not use a data monitoring committee.

##### **7.1.3. Final Analysis**

The FA will be performed at the end of study. Before the FA, all data will be cleaned and the database will be locked/released. Some specified endpoints will be summarized newly or updated from the PA at the FA.

#### 7.1.4. Periodic Safety Review

For the purposes of this study, Pfizer procedures for periodic safety review will be applied by an internal safety review team with medical and statistical capabilities.

### 7.2. Interim Analyses and Summaries

#### 7.2.1. Interim Look

##### 7.2.1.1. Timing of the Interim Look

The IL will occur at 3 months after the first dose of the last patient.

##### 7.2.1.2. Endpoints

The following endpoints for patients with sufficient follow-up will be summarized at the IL:

- Cumulative incidence of MMR at 12 months;
- MMR by 12 months;
- MMR at 3, 6 and 9 months;
- MR^1 at 3 months;
- all safety endpoints;
- All PK endpoints except for primary endpoint related parameters (Exposure-Response relationship will not be included in the interim data.), and
- Baseline variables.

Analysis of primary endpoint will not be conducted at the IL.

##### 7.2.1.3. Hypotheses

No statistical hypothesis test will be performed. Therefore, no alpha will be spent at the IL.

##### 7.2.1.4. Analysis Sets

###### 7.2.1.4.1. Efficacy

For efficacy endpoints, the modified as-treated population will be used at the IL. In addition, a specified subset of the modified as-treated population shown below will also be used in each endpoint if specified.

Endpoints	Subset Criteria

• Cumulative incidence of MMR at 12 months

• MMR by 12 months

	

• For the patient continuing the study treatment, the assessment at 12 months is completed.

• For the patient discontinuing the study treatment, at least 332 days after the first dose of study drug in the patient have passed at the IL.

Endpoints	Subset Criteria

 
• MMR at 6 months
 
	
 
• For the patient continuing the study treatment, the assessment at 6 months is completed.
 
• For the patient discontinuing the study treatment, at least 164 days after the first dose of study drug in the patient have passed at the IL.
 

 
• MMR at 9 months
 
	
 
• For the patient continuing the study treatment, the assessment at 9 months is completed.
 
• For the patient discontinuing the study treatment, at least 248 days after the first dose of study drug in the patient have passed at the IL.
 

